13 DATA HANDLING AND RECORD KEEPING

13.1 Case Report Forms

All patient data generated by the study will be recorded in each patient's CRFs. Data reported on the CRFs that are derived from source documents should be consistent with the source documents or the discrepancies should be explained. CRFs will be considered complete when all missing and/or incorrect data have been resolved and all safety data have been recorded.

The Investigator, or designated representative, should complete the CRF as soon as possible after information is collected. CRFs must be completed only by persons designated by the Investigator. The completed CRF will be reviewed by Laurent Pharmaceuticals or its agents on a routine basis.

The Investigator must approve formally all the information in the CRFs for the patients for whom he/she is responsible. The United States Food and Drug Administration (FDA) or Health Canada may inspect all records related to the study.

13.1.1 Source Documentation

Source documents are considered to be all information in original records and certified copies of original records of clinical findings, observations, data, or other activities in a clinical study necessary for the reconstruction and evaluation of the study. The Investigator and designees agree to maintain accurate e-CRFs and source documentation as part of the case histories. Source documents are the originals of any documents used by the Investigator, sub-Investigator, or hospital/institution that will allow verification of the existence of the patient and substantiate the integrity of the data collected during the trial. All data entered into the CRF also must be available in the source documents. The Investigator will allow designated representatives of Laurent Pharmaceuticals, IRB/IEC and regulatory bodies, including the FDA to have direct access to the source documents to verify the data reported in the CRFs. Personally identifiable source documentation shall not be copied or removed from the Investigator site, and to the extent permitted by law and/or regulations, will not be made publicly available. All representatives of Laurent Pharmaceuticals, IRB/IEC and regulatory bodies must respect confidentiality.

13.1.2 Record Retention

Study records and source documents need to be preserved for at least 15 years after the completion or discontinuation of/withdrawal from the study, or 2 years after the last approval of a marketing application in an International Conference on Harmonization (ICH) region, whichever is the longest time period.

14 MONITORING

In accordance with current applicable regulations, Good Clinical Practice (GCP), and Laurent Pharmaceuticals procedures, monitors will contact the site before the start of the study to review with the site staff the protocol, study requirements, and their responsibilities to satisfy regulatory, ethical, and Laurent Pharmaceuticals requirements. When reviewing procedures for data collection, the discussion will include identification, agreement, and documentation of data items which will be recorded in each patient's CRF.

The study will be monitored to ensure the following:

- Data are authentic, accurate, and complete;
- The safety and rights of patients are being protected;
- The study is being conducted in accordance with the currently approved protocol, any other study agreements, GCP, and all applicable regulatory requirements.

The Investigator and the head of the medical institution (where applicable) agree to allow the monitor direct access to all relevant documents.

15 QUALITY CONTROL AND QUALITY ASSURANCE

The sponsor or its designee will perform the quality assurance and quality control activities of this study. However, responsibility for the accuracy, completeness, and reliability of the study data presented to Laurent Pharmaceuticals lies with the principal or qualified Investigator generating the data.

Laurent Pharmaceuticals or its designated representative will conduct a in-person or remote study site visit to verify the qualifications of the principal Investigator and sub-Investigators, may inspect clinical site facilities as needed, and inform the Investigator of responsibilities and procedures for ensuring adequate and correct study documentation. During COVID-19-related site restrictions, some site qualification and initiation activities may be carried out remotely, with study documentation supporting in lieu the qualification until the time allows in-person confirmation to happen.

Instances of missing, discrepant, or uninterpretable data will be queried with the Investigator for resolution. Any changes to study data will be enacted in the CRF and documented in an audit trail, which will be maintained within the clinical database.

16 COMPLIANCE, PROTOCOL AMENDMENT AND DEVIATION

16.1 Compliance

It is very important that no modifications to the protocol should be made without the approval of Laurent Pharmaceuticals and Investigators. Changes that significantly affect the safety of the patients, the nature, the scope and the scientific integrity of the study will require IRB/IEC notification/approval before their implementation. Exceptions are cases where the modification is necessary to abrogate an apparent immediate risk to the patients. Laurent Pharmaceuticals or designee will submit all protocol modifications to IRB/IEC and the required regulatory authorities. When there is a need for immediate deviation from procedures enunciated in the protocol, the Investigator will contact Laurent Pharmaceuticals to discuss the course of action and possible alternatives, if at all possible, before any implementation of changes. Any deviation from protocol must be fully documented in the source documentation and in the study documentation on protocol deviations.

16.2 Protocol Amendment

Administrative amendments to the protocol will be classified as amendments of typographical errors, clarifications of confusing wording, name changes, and minor modifications that have no impact on the safety LAU-7b for the treatment of COVID-19 disease in Adults

Amendment 5, V2.4, Aug 4th, 2023

71 of 79

of the patients or the science of the study. Administrative amendments will be submitted to the IRB/IEC for information only. Laurent Pharmaceuticals will ensure that acknowledgement is received and filed. Any other amendment will be classified as a substantial amendment and will be submitted to the appropriate regulatory authorities and the IRBs/IECs for approval.

16.3 Protocol Deviation

Should a protocol deviation occur, Laurent Pharmaceuticals must be informed as soon as possible. Important protocol deviations and their reasons will be summarized in the clinical study report. In accordance with applicable regulatory authority mandates, the investigator is responsible for reporting protocol deviations to the IRB/IEC.

17 STUDY TERMINATION

At any time, Laurent Pharmaceuticals may terminate this study in its entirety or at specific clinical site. In addition, for reasonable cause, the IRB/IEC and/or the Investigator at a clinical site may terminate the study at their center. In such cases, Laurent Pharmaceuticals should be informed immediately and if at all possible, before implementation.

Conditions that may lead to reasonable cause and warrant termination include, but are not limited to:

- Investigator noncompliance and/or lack of adherence to protocol procedures;
- Unsatisfactory patient enrollment;
- Lack of evaluable and/or complete data;
- Potentially unacceptable risk to patients (see Section 7.2.3 for additional guidance);
- Changes in Laurent Pharmaceuticals drug development plans;
- Decision by the FDA or Health Canada.

The reason(s) for clinical study termination must be properly documented.

18 ETHICAL CONSIDERATIONS

The study will be conducted according to current GCP, including any future revisions, all relevant local laws and regulations, as well as the principles of the Declaration of Helsinki and its amendments. IRB/IEC committees will review and approve this protocol and informed consent. All patients must provide written informed consent where applicable, before participation in the study.

This study will be performed by qualified clinical investigators and in accordance with GCP. The study specifically incorporates all of the following features:

- Multicenter, randomized study design;
- Prospectively stated objectives and analytical plan;
- Accepted, pre-specified outcome measures for safety and efficacy;
- Investigator meeting (or equivalent) prior to study start and a detailed protocol to promote consistency across sites;
- Compliance with current GCP, with assessment via regular monitoring;

• Quality assurance procedures performed at study sites and during data management to ensure that safety and efficacy data are adequate and well documented.

The study will only be conducted at sites where IRB/IEC approval has been obtained. The protocol, Investigator's Brochure, sample ICF, advertisements (if applicable), written information given to the patients, safety updates, annual progress reports, and any revisions to these documents will be provided to the IRB/IEC by the investigator or Laurent Pharmaceuticals, as allowable by local applicable laws and regulations.

19 FINANCING AND INSURANCE

Financial aspects of the study are addressed in a separate clinical study agreement.

The Investigator/institution is required to have adequate current insurance to cover claims for negligence and/or malpractice according to national regulations. Laurent Pharmaceuticals will provide insurance coverage for the clinical study as required by national regulations.

20 PUBLICATION POLICY AND CLINICAL STUDY REPORT

20.1 Confidentiality and Publication Policy

Both the use of data and the publication policy are detailed within the clinical study agreement.

Any and all scientific, commercial, and technical information disclosed by Laurent Pharmaceuticals in this protocol or any other documents and communications should be considered the confidential and proprietary property of Laurent Pharmaceuticals. The Investigator shall hold such information in confidence and shall not disclose the information to any third party except to the Investigator's staff on a "need to know" basis, as long as the said staff has been made aware that the information is confidential and who are bound to treat it as such.

The Investigator shall not use any and all information for any purpose other than determining interest in performing the study and, if the parties decide to proceed with the study, for the purpose of conducting the study. The Investigator understands that the information developed from this clinical study will be used by Laurent Pharmaceuticals for the development of the study drug and therefore may be disclosed as required to other clinical Investigators, potential and current business partners and associates, Health Canada, the FDA, and possibly other agencies, without bearing any personally identifiable information. The Investigator also understands that, to allow for the use of the information derived from the clinical study, he/she has the obligation to provide Laurent Pharmaceuticals with complete results and accompanying data developed in the study.

No publication or disclosure of study results will be permitted except under the terms and conditions of a separate written agreement between Laurent Pharmaceuticals and the Investigator and/or the Investigator's institution. In all instances, personally and individually identifiable information shall not be published.

20.2 Clinical Study Report

A clinical study report, written in accordance with the ICH E3 Guideline, will be submitted in accordance with local regulations.

I have reviewed the Statistical Analysis Plan Addendum. My signature below confirms my agreement with the contents and intent of this document.							
Reviewed by:							
		Date:					
		Date:					

Project Code #: [Enter Project Code] Date: October 29, 2024

Status: Version 1.0

1. Introduction

This document is an addendum to the Statistical Analysis Plan (SAP) for protocol LAU-20-01, entitled "Resolution: A Double-Blind, Randomized, Placebo-Controlled, Phase II/III Study Of The Efficacy And Safety Of LAU-7b In The Treatment Of Adult Hospitalized Patients With COVID-19 Disease". The analyses as planned in the SAP were completed following database lock, and the results initially released on 14MAR2024.

The primary endpoint for this study is the proportion of patients requiring mechanical ventilation AND/OR deceased (all causes) by Day 60. Missing observations are treated as a non-response (i.e. patient not considered as alive and free of respiratory failure) for the primary analyses on ITT. Other imputations of missing data are included as sensitivity analyses.

Following the release of the results and review of the draft Clinical Study Report (CSR), the sponsor determined that the imputation method specified in the protocol (Section 12.7.1) and the SAP (Section 6.4.1) for handling missing data in the primary endpoint analysis was implausible from a clinical perspective. Specifically, treating all missing observations as non-response by assigning patients to the worst possible health status categories (i.e. not considered as alive and free of respiratory failure) was deemed overly conservative and unreflective of patients' actual health conditions. The sponsor hence proposed a revised approach to imputation for the primary analysis. The new method will treat missing observations as is, without any imputation, i.e. Including all patients with available health status/survival data at Day 60 for the primary analysis. Several additional analyses of efficacy outcomes were also requested for better understanding and interpretation of the data.

This SAP addendum serves to formally document the changes to the imputation method for the primary analysis of the primary endpoint, and the additional analyses as requested by the sponsor. For a complete description of the analysis for this study, please refer to the Statistical Analysis Plan (SAP), dated 29SEP2023.

2. Primary Endpoint Analysis

The primary analysis for the primary endpoint will treat missing observations as is without any imputation, i.e. Including all patients with available health status/survival data at Day 60 for the primary analysis. This is the complete case analysis.

The results from this approach will be presented as the primary analysis in the CSR, while the original analysis using the imputation method specified in the protocol and the SAP will still be included in the CSR, but referred to as the "former planned primary analysis".

3. Additional Analyses

The updated imputation method is defined as follows:

- For the primary analyses on the intent-to-treat (ITT) population, missing observations will not be imputed.
- The original method, which assigned missing observations to non-response (health status 6-7), will continue to be reported as part of the CSR to ensure full transparency.
- The sensitivity and supplementary analyses will remain the same.
- The table numbering follows the ICH E3 guideline for CSR. Since both the pilot study and the extension study are included in the CSR, along with the additional tables described in this SAP addendum, the numbering rule is described as follows:
 - o Main tables from the pilot study are numbered without any suffix.
 - Main tables from the extension study are numbered with the suffix "e".
 - Additional tables described in this SAP addendum are numbered with ".1e" replacing the suffix "e".
- The impacted tables to be differentiated from the main tables in the extension study are listed below:
 - Table 14.2.1.1.1e Primary Analysis: Proportion of Patients Requiring Mechanical Ventilation (includes ECMO) and/or Deceased by Day 60 – ITT;
 - Table 14.2.1.4.1e Supplemental Analysis: Proportion of Patients Requiring Mechanical Ventilation (includes ECMO) and/or Deceased by Day 60 Analyzed by Logistic Regression;
 - Table 14.2.3.1.1e Proportion of Patients Alive and Free of Respiratory Failure on Day 29 ITT;
 - Table 14.2.3.2.1e Proportion of Patients Alive and Free of Respiratory Failure on Day 29 PP;

Status: Version 1.0

Protocol Number: LAU-20-01

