12 STATISTICAL ANALYSIS

A statistical analysis plan (SAP) will provide details of the methods of analysis to address all study objectives. The SAP may be amended during the course of the study, but will be finalized before the cutoff date for any analysis, interim or final.

Data summaries by treatment group will be presented. For categorical data such as the 7-point Ordinal Scale, data will be tabulated in frequency tables to display the number and proportion of patients for each category by treatment group. For continuous variables, data will be summarized with the number of patients, mean, standard deviation, median, and minimum and maximum values by treatment group. Baseline assessments for each outcome variable will be defined as the screening measurement unless a repeat value was obtained, see restrictions in Section 9.2.1.1, before the first dose of study drug. Statistical significance will be set at the 5% level (one-sided) for the pilot portion and at the 5% level (two-sided) for the extension. Consideration

will be given for adjusting for pre-specified prognostic baseline factors such as age, the ordinal scale health status at baseline and comorbidities, where applicable.

Diligent efforts will be made to prevent missing data in the study. For example, patients who discontinue the study treatment early should still be followed for all regularly scheduled visits for safety and relevant efficacy assessments, until the Day 60 follow-up. A clear distinction should be made between treatment discontinuation and study withdrawal. Efficacy assessments occurring after treatment discontinuation should not be included in the per-protocol analysis.

Database lock and statistical analyses will be performed for the pilot portion and the extension, separately.

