Population-Level Summary	The proportion of patients requiring mechanical ventilation (includes ECMO) AND/OR deceased by Day 60 will be analyzed using a Fisher		

	exact test to compare proportion of LAU-7b treated subjects relative to placebo.
Estimand Description	Superiority of LAU-7b on the proportion of patients requiring mechanical ventilation or deceased by Day 60 will be analyzed using Fisher exact test irrespectively from the interruption of treatment, early discontinuation of the treatment (for other reason than death) or use of disallowed medication.
Imputation/Data/Censoring Rule(s)	Missing observations will be treated as a non-response (i.e. patient considered as Health Status 6-7 inclusively) for the primary analyses on ITT.
Sensitivity Analysis	Sensitivity analyses where missing observations will be imputed using different methods will also be performed and will be further detailed in the SAP.

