12.7 Efficacy Analysis

12.7.1 Analysis of Primary Endpoint

The proportion of patients requiring mechanical ventilation (includes ECMO) AND/OR deceased by Day 60 will be analyzed using a Chi-Square test (or a Fisher exact test if the expected values in any of the cells of the contingency table are below 5).

Logistic regression including treatment group, age group and other prognostic factors at baseline will also be performed.

Missing observations will be treated as a non-response (i.e. patient not considered as alive and free of respiratory failure) for the primary analyses on ITT. Sensitivity analyses where missing observations will be imputed using different methods will also be performed and will be further detailed in the SAP.

Additional post-hoc analyses may be performed in an exploratory manner depending on the frequency of other phenotypes or concomitant drugs.

Full details will be specified in the SAP and its Addendum dedicated to the study expansion.

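### The SAP addendum makes a complete-case analysis the primary analysis after the results were released, displacing the pre-specified missing = non-response analysis

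*SAP*

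**What the plan says.** Protocol 12.4, Table 3, sets the rule for the primary analysis: "Missing observations will be treated as a non-response (i.e. patient considered as Health Status 6-7 inclusively) for the primary analyses on ITT". Section 12.7.1 repeats it with a different gloss: "Missing observations will be treated as a non-response (i.e. patient not considered as alive and free of respiratory failure". Both sections leave other ways of handling missing data to sensitivity analyses. By the addendum's account, SAP section 6.4.1 carries the same rule. Protocol section 12 lets the SAP be amended, but says it "will be finalized before the cutoff date for any analysis, interim or final".

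The addendum (version 1.0, 29 October 2024) gives its own chronology. In section 1: "The analyses as planned in the SAP were completed following database lock, and the results initially released on 14MAR2024". Then: "Following the release of the results and review of the draft Clinical Study Report (CSR), the sponsor determined that the imputation method" was clinically implausible and too conservative. Section 2 makes the complete-case analysis primary, "Including all patients with available health status/survival data at Day 60 for the primary analysis", and adds: "The results from this approach will be presented as the primary analysis in the CSR". The planned analysis stays in the report, relabelled as the former one. Section 3 lists the affected tables, headed by "Table 14.2.1.1.1e Primary Analysis: Proportion of Patients Requiring Mechanical Ventilation (includes ECMO) and/or Deceased by Day 60". The others are the supplemental logistic regression and the Day 29 tables for ITT and PP.

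**The concern.** The two-sided 5% level in protocol section 12 belongs to the analysis fixed before the data were seen. If the sponsor may choose the primary analysis after reading the results, the p-value with that label no longer has a known error rate. The label matters here: protocol 5.4.3.2 calls the extension confirmatory and says it may support an Emergency Use Authorization application.

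The switch also changes the assumption about missing patients, from all having had the event to resembling those observed. With about nine events expected in one arm and none in the other, that assumption alone can decide significance.

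A second, smaller problem is the analysis set. The endpoint is an event by Day 60, but the new set is patients with data at Day 60. Read literally, a patient seen to be ventilated and later lost to follow-up is dropped although the event is known. The addendum does not say whether that is intended.

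**Working it through.** **Timing.** The SAP is dated 29 September 2023, results were released on 14 March 2024, and the addendum is dated 29 October 2024. From 14 March to 29 October 2024 is 229 days. The change therefore falls after the point at which protocol section 12 requires the SAP to be final.

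**Plan's own figure.** Inputs from protocol 12.1: 132 per arm, 7% vs 0%, two-sided Fisher exact test, alpha 0.05. With 0 events on LAU-7b and k on placebo, p = 2·C(132,k)/C(264,k). This gives 0.060 for k = 5 and 0.029 for k = 6. Power is P(X ≥ 6) with X ~ Binomial(132, 0.07), which is 90.6%. The planned sample size reproduces.

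**Illustration 1: can the choice decide the verdict?** The expected placebo count is 0.07 × 132 = 9.24, so take 0 vs 9 observed events. Assume m event-free patients are missing in each arm.
- Planned rule: compare m/132 with (9 + m)/132.
- Complete case: compare 0/(132 − m) with 9/(132 − m).
- Table 3 names Fisher. Section 12.7.1 names chi-square, with Fisher if any expected cell is below 5. Both were run (chi-square without continuity correction).

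| Missing per arm, m | Planned rule, Fisher p | Planned rule, 12.7.1 p | Complete-case p |
|---|---|---|---|
| 0 | 0.003 | 0.003 | 0.003 |
| 4 (3.0%) | 0.042 | 0.024 | 0.003 |
| 5 (3.8%) | 0.054 | 0.032 | 0.003 |
| 6 (4.5%) | 0.067 | 0.041 | 0.003 |
| 7 (5.3%) | 0.079 | 0.0495 | 0.003 |
| 8 (6.1%) | 0.091 | 0.059 | 0.003 |

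Complete-case p stays at 0.003 up to m = 14. The smallest expected cell is then 9/2 = 4.5, so 12.7.1 also selects Fisher for it. The verdicts part from 5 missing per arm with Fisher and from 8 under 12.7.1. Below those counts they agree.

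**Illustration 2: upper case under the null.** Simulation of 40,000 trials per setting, 132 per arm, equal true event rates of 5% or 7%, and 2%, 5% or 10% missing at random (rates assumed). Two-sided rejection at 0.05:

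| | Fisher | 12.7.1 rule |
|---|---|---|
| Planned analysis alone | 2.6–3.5% | 4.7–5.1% |
| Success on either analysis | 4.1–5.9% | 6.7–8.4% |
| The two analyses disagree | 2.4–5.1% | 4.0–7.3% |

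The middle row assumes that success would be claimed on whichever analysis is significant. The documents state no such rule, so this is a ceiling for these settings and not an estimate.

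**The case against.** The best defence is that the addendum hides nothing. It dates the change, gives a clinical reason, keeps the planned result in the report, and leaves the sensitivity and supplementary analyses as they were. A reader can recover the planned analysis.

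The reason also has statistical substance. If missing patients are mostly event-free, counting them as events dilutes the contrast. With 7% vs 0% among observed patients and equal missingness, Fisher power at 132 per arm falls from 90.6% to 61% at 2% missing and 41% at 5%. Complete case keeps 89.5% and 87.7%. Used alone, complete case rejects 3.0–3.6% (Fisher) or 4.2–5.0% (12.7.1) of null trials, so it is not an invalid test in itself. Counting only wins for LAU-7b, with event rates of 3.5% or 7% and 5% or 10% missing, the either-analysis Fisher rate is 2.4–3.1% against a nominal 2.5%.

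All of that stands, and it limits what can be said about numerical inflation. It does not answer the point about timing. That the rule is conservative could have been argued from the plan alone, without seeing results: the rule stands in protocol Amendment 5 of August 2023, written after the pilot. The defect lies in when the choice was made.

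It is also fair that the Day 29 tables concern a secondary endpoint, that the logistic regression is already titled supplemental, and that the September 2023 SAP, which was not available for this review, may define how an observed event followed by loss is counted. These are points of labelling and clarification and are secondary to the main finding.

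**Conclusion.** The concern holds. The addendum itself shows that the primary analysis was replaced after results were released and the draft report reviewed, contrary to protocol 12, 12.4 and 12.7.1. The complete-case p-value cannot carry the planned 5% level.

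The practical size is unknown, because the documents give no missing counts, results or decision rule. It is not claimed that the conclusion changed. On the plan's own effect, with equal and event-free missingness assumed, 5 missing per arm (Fisher) or 8 (12.7.1) are enough for the two analyses to give opposite verdicts. In the upper-case null simulation, error stays close to nominal with Fisher and reaches 8.4% under 12.7.1. The finding rests on the status of the analysis and does not depend on these figures. It must be fixed because it governs the trial's headline inference.

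**What to change.** - In addendum section 2 and the CSR, keep missing = non-response as the primary analysis. By the addendum's numbering rule its main extension table should be 14.2.1.1e.
- Retitle Table 14.2.1.1.1e as a complete-case analysis promoted after results were known: post hoc, or sensitivity if the SAP of 29 September 2023 already listed it. Label Tables 14.2.1.4.1e, 14.2.3.1.1e and 14.2.3.2.1e in the same way.
- Add one derivation sentence: any ventilation, ECMO or death observed through Day 60 counts as an event, and only event-free patients with unknown Day 60 status are excluded.
- Optional: if worst-case imputation is thought implausible, report missing counts and reasons by arm with a tipping-point analysis, labelled post hoc unless already planned.

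The cost is relabelling, one sentence and, if wanted, one extra analysis. No new data are needed. The headline then rests on the planned analysis, whose result the documents do not report. It may be less favourable, and under the plan's assumptions it has less power once patients are missing.
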